#### Statement of Compliance to protocol, GCP and applicable regulatory guidelines:

This trial will be conducted in compliance with the protocol, ISO 14155, the International Conference on Harmonization Good Clinical Practice E6 (ICH-GCP), the Declaration of Helsinki, and all applicable regulatory requirements.

### **CHANGE HISTORY**

Version	Originator	Description of Change(s) and Section Number(s) Affected	Date
1.0	[name]	Original Protocol	06 May 2020
2.0	[name]	Corrected repeat steps numbers in the section 7.2 of step 1.28; Updated	21 July 2020
		labeling protocol numbers; added COVID Risk Mitigation appendix	

#### **SYNOPSIS**

[figure not shown]
Protocol Title	Evaluation of Visual Performance of Two Types of Cosmetic Contact Lenses	
Sponsor	JJVC, [name]	
Clinical Phase	Confirmatory, Phase 3	
Trial Registration	This study will be registered on ClinicalTrials.gov based on the following: confirmatory study meets the requirements for registration.	
Test Article(s)	Investigational Products: etafilcon A with cosmetic pattern Approved Products: 1-DAY ACUVUE® DEFINE® Vivid style	
Wear and Replacement	Wear Schedule: Daily Wear	
Schedules	Replacement Schedule: Daily Disposable	
Objectives	Primary Objective:	
	The primary objective.  The primary objective of this study is to evaluate the Distance Monocular logMAR visual performance of the Investigational Cosmetic Contact Lenses manufactured in etafilcon A material (Test) in comparison to 1-Day Acuvue Define Vivid Style (Control), manufactured in etafilcon A material.	
	Exploratory Objectives: Additional objectives include lens fit, ocular symptoms, and slit-lamp findings	
Study Endpoints	Primary endpoint:  1. Distance Monocular logMAR visual performance (high luminance low contrast and low luminance high contrast)	
	Other observations:	
	1. Mechanical Lens fit	
	2. Cosmetic Lens fit/Hula Hoop	
	3. Ocular Physiology	
Study Design	This is a single visit, brand-masked, non-dispensing, 2×2 bilateral crossover study. Each subject will be bilaterally fitted with one of the two test articles in each of the study periods in a random order.	
	See the flow chart at the end of the synopsis table for the schematic of the study visits and procedures of main observations.	
Sample Size	Up to 40 subjects will be enrolled with the aim of approximately 34 subjects completing.	
Study Duration	The study is expected to last up to 1 month. The enrollment period will also be up to 3 weeks.	

Anticipated Study	We will aim to recruit up to 40 habitual contact lens wearing	
Population	subjects, ages 18 to 39 (inclusive).	
Eligibility Criteria	Potential subjects must satisfy all of the following criteria to be enrolled in the study:  1. The subject must read, understand, and sign the STATEMENT OF INFORMED CONSENT and receive a fully executed copy of the form  2. Appear able and willing to adhere to the instructions set forth in this clinical protocol  3. Subjects between 18 and 39 (inclusive) years of age at the time of screening  4. Be a current soft contact lens wearer in both eyes with a minimum of 6 hours/day and 5 days/week over the last month by self-report  5. The subject must be willing to be photographed and/or video-taped  Eligibility after Baseline:  6. The subject's vertex corrected spherical equivalent distance refraction must be in the range of -1.00 D to -6.00 D (inclusive) in each eye  7. The subject's refractive cylinder must be less than or equal to 0.75 D (inclusive) in each eye  8. Have spherical best corrected visual acuity of 20/25 or better in each eye	

	Potential subjects who meet any of the following criteria will
	be excluded from participating in the study:
	1. Currently pregnant or lactating
	2. Any systemic disease (eg, Sjögren's Syndrome),
	allergies, infectious disease (eg, hepatitis,
	tuberculosis), contagious immunosuppressive diseases
	(eg, HIV), autoimmune disease (eg rheumatoid
	arthritis), or other diseases, by self-report, which are
	known to interfere with contact lens wear and/or
	participation in the study (at the investigators
	discretion)
	3. Use of systemic medications (eg, chronic steroid use)
	that are known to interfere with contact lens wear (at
	the investigators discretion)
	4. Any previous, or planned (during the study) ocular
	surgery (eg, radial keratotomy, PRK, LASIK, etc.)
	5. Participation in any contact lens or lens care product
	clinical trial within seven (7) days prior to study enrollment.
	6. Employee or family members of clinical site (eg,
	Investigator, Coordinator, Technician) Exclusion
	Criteria after Baseline
	Eligibility after Baseline:
	7. Any ocular allergies, infections or other ocular
	abnormalities that are known to interfere with contact
	lens wear and/or participation in the study. This may
	include, but not be limited to entropion, ectropion,
	extrusions, chalazia, recurrent styes, glaucoma, history
	of recurrent corneal erosions, aphakia, or corneal
	distortion (at the investigators discretion)
	8. Clinically significant (Grade 3 or 4 on FDA scale)
	tarsal abnormalities, bulbar injection, corneal edema,
	corneal vascularization, corneal staining, or any other
	abnormalities of the cornea which would
Disallary 1	contraindicate contact lens wear.
Disallowed Medications/Interventions	None
Measurements and	logMAD vigual aquity long fit aggregation to aggregate long fit
Procedures	logMAR visual acuity, lens fit assessment, cosmetic lens fit
Tiocedules	assessment/hula hoop assessment, and safety parameters (slit lamp findings, entrance/exit visual acuity).
Microbiology or Other	None
Laboratory Testing	TYORC
Laboratory resumg	

Study Termination	The occurrence of one or more Unanticipated Adverse
	Device Effect (UADE), or any SAE where relationship to
	study agent cannot be ruled out, will result in stopping
	further dispensing investigational product. In the event of a
	UADE or SAE, the Sponsor Medical Monitor may unmask
	the treatment regimen of subject(s) and may discuss this with
	the Principal Investigator before any further subjects are
	enrolled.
Ancillary Supplies/ Study-	Tears Naturale re-wetting drops, FluStrips fluorescein strips,
Specific Materials	Bausch & Lomb Sensitive Eyes plus Saline, or alternative
	products approved by the Sponsor.
Principal Investigator(s)	A full list of Principal Investigators, clinical sites, and
and Study	institutions is kept separately from the Study Protocol and is
Institution(s)/Site(s)	included in the study Trial Master File.

Figure 1: Study Flowchart

#### COMMONLY USED ABBREVIATIONS AND DEFINITIONS OF TERMS

ADD Plus Power Required For Near Use

ADE Adverse Device Effect

AE Adverse Event/Adverse Experience
BCVA Best Corrected Visual Acuity

BSCVA Best Spectacle Corrected Visual Acuity

CFR Code of Federal Regulations
CLUE Contact Lens User Experience

COAS Complete Ophthalmic Analysis System

COM Clinical Operations Manager CRA Clinical Research Associate

CRF Case Report Form

CRO Contract Research Organization

CT Center Thickness

D Diopter

DMC Data Monitoring Committee eCRF Electronic Case Report Form EDC Electronic Data Capture

ETDRS Early Treatment Diabetic Retinopathy Study

FDA Food and Drug Administration

GCP Good Clinical Practice

HIPAA Health Insurance Portability and Accountability Act

IB Investigator's Brochure ICF Informed Consent Form

ICH International Conference on Harmonization

IDE Investigational Device Exemption IEC Independent Ethics Committee IRB Institutional Review Board

ISO International Organization for Standardization

ITT Intent-to-Treat

JJVC Johnson & Johnson Vision Care, Inc.

LC Limbus Center

LogMAR Logarithm of Minimal Angle of Resolution MedDRA© Medical Dictionary for Regulatory Activities

MOP Manual of Procedures

NIH National Institutes of Health

OD Right Eye

OHRP Office for Human Research Protections
OHSR Office for Human Subjects Research

OS Left Eye
OU Both Eyes

PD Protocol Deviation

PHI Protected Health Information

PI Principal Investigator

PIG Patient Instruction Guide PQC Product Quality Complaint PRO Patient Reported Outcome

QA Quality Assurance QC Quality Control

qCSF Quick Contrast Sensitivity Function

qVA Quantitative Visual Acuity

SAE Serious Adverse Event/Serious Adverse Experience

SAP Statistical Analysis Plan SAS Statistical Analysis System

SD Standard Deviation

SOP Standard Operating Procedure

UADE Unanticipated Adverse Device Effect

USADE Unanticipated Serious Adverse Device Effect

VA Visual Acuity

#### 1. INTRODUCTION AND BACKGROUND

Cosmetic contact lenses can have patterns of varying size and opacities. When designing these cosmetic patterns, it is important to allow a sufficient clear area in the center of the lens optical zone so that the wearer's vision is not negatively impacted by the pattern.

In the current study, we will assess the objective visual performance of an investigation cosmetic soft contact lens compared to an approved cosmetic soft contact lens.

#### 1.1. Name and Descriptions of Investigational Products

This study will include two types of cosmetic contact lenses. The Control lens, 1-DAY ACUVUE® DEFINE® Vivid style is an approved product, the Test, Etafilcon A Investigational Cosmetic Contact Lenses with PVP, is an investigational product. Further details about the test articles are found in Section 6 of this protocol.

#### 1.2. Intended Use of Investigational Products

The intended use of the investigational product is to correct vision. The investigational product contains a cosmetic pattern, so it also affects the visual appearance of the eye. During this non-dispensing study, each lens type will be worn for approximately 90 minutes.

#### 1.3. Summary of Findings from Nonclinical Studies

All previous pre-clinical findings were deemed satisfactory prior to proceeding with clinical trials on humans. For the most comprehensive nonclinical information regarding etafilcon A cosmetic contact lenses refer to the latest version of the Investigator's Brochure (Etafilcon A Investigational Limbal Ring Contact Lenses with polyvinylpyrrolidone [PVP]).

#### 1.4. Summary of Known Risks and Benefits to Human Subjects

The following risks/adverse events can be associated with wearing soft contact lenses in general:

- The eyes may burn, sting and/or itch.
- There may be a feeling of something in the eye (foreign body, scratched area).
- There may be the rare potential for some temporary impairment due to peripheral infiltrates, peripheral corneal ulcers and corneal erosion.
- There may be the rare potential for other physiological observations, such as local or generalized edema, corneal neovascularization, corneal staining, injection, tarsal abnormalities, iritis and conjunctivitis, some of which are clinically acceptable in low amounts.
- There may be excessive watering, unusual eye secretions, or redness of the eye.
- Poor visual acuity, blurred vision, rainbows or halos around objects, photophobia, or dry eyes may also occur if the lenses are worn continuously or for too long a time.
- Due to the reduction in light transmittance with cosmetically tinted lenses, some patients may experience visual symptoms while wearing the Study Contact Lenses. In addition, some patients may experience reduced peripheral awareness due to the opaque iris pattern.

There is no direct benefit to the subjects for participating in the study, although they will be able to try out marketed and investigational cosmetic contact lenses. The information from this study will aid if the further development and assessment of new potential cosmetic contact lenses.

For the most comprehensive clinical information regarding etafilcon A cosmetic contact lenses with PVP and the marketed contact lenses refer to the latest version of the Investigator's Brochure (Etafilcon A Investigational Limbal Ring Contact Lenses with PVP) and the package insert (APPENDIX C: PACKAGE INSERT (APPROVED PRODUCT).

# 1.5. Relevant Literature References and Prior Clinical Data Relevant to Proposed Clinical Study

There have been no serious or unanticipated adverse events and no loss of best correct VA reported in previous etafilcon A with PVP cosmetic contact lens clinical studies. There was one significant adverse event in which was a small non-staining white corneal lesion. The site deemed this as not related to the study lenses as it was present prior to enrollment and stable at the final evaluation. See Clinical Study report for more information on this finding.

For the most comprehensive clinical information regarding etafilcon A cosmetic contact lenses with PVP and the marketed contact lenses refer to the latest version of the Investigator's Brochure (Etafilcon A Investigational Limbal Ring Contact Lenses with PVP) and the package insert (APPENDIX C: PACKAGE INSERT (APPROVED PRODUCT).

#### 2. STUDY OBJECTIVES, ENDPOINTS AND HYPOTHESES

#### 2.1. Objectives

#### Primary Objective

The primary objective of this study is to evaluate the Distance Monocular logMAR visual performance of the Investigational Cosmetic Contact Lenses manufactured in etafilcon A material (Test) in comparison to 1-Day Acuvue Define Vivid Style (Control), manufactured in etafilcon A material.

#### **Exploratory Objectives**

Additional objectives include assessments of mechanical and cosmetic lens fit, subject reported ocular symptoms, and slit-lamp findings.

#### 2.2. Endpoints

#### Primary endpoints

#### Distance Monocular Visual Performance (logMAR)

#### Other Endpoints

#### Mechanical Lens fit

Lens fitting will be assessed in each eye using a slit-lamp post lens fitting; Lens fitting characteristics to be reported are:

- Lens Centration Grade
- Decentered Direction
- Limbal Exposure Grade
- Edge Lift (Present or Absent)
- Primary Gaze Movement Grade
- Upgaze Movement Grade
- Lens Tightness Grade (Push-up Test)
- Acceptable Fitting (yes/no)

#### Cosmetic Lens fit

Cosmetic lens fit assessment will be performed in each eye at post lens fitting by the investigator without the use of a slit-lamp at a distance of approximately 3 feet from the subject in:

- Primary Gaze
- Extreme Gaze (left and right)
- Extreme Up-gaze

#### Hula Hoop

If an investigator observes an unacceptable cosmetic lens fit in any gaze, a hula hoop assessment will be performed post lens fitting by the investigator without the use of a slit-lamp at a distance of approximately 3 feet from the subject in:

- Primary Gaze
- Extreme Gaze (left and right)
- Extreme Up-gaze

#### Ocular Physiology

Slit lamp findings will be assessed for each subject eye at baseline and the exit evaluation using the FDA Grading scale (Grade 0=None, Grade 1=Trace, Grade 2=Mild, Grade 3=Moderate, Grade 4=Severe). Slit lamp finding assessments include the following metrics:

- Corneal Infiltrates (Yes/No)
- Corneal Edema
- Corneal Neovascularization
- Corneal Neovascularization Location
- Corneal Staining
- Corneal Staining Location
- Conjunctival Injection
- Tarsal Abnormalities
- Other

#### 2.3. Hypotheses

**Primary Hypotheses** 

Both primary hypotheses must be met in order to satisfy the objective of the study.

- 1. The Test lens will be non-inferior to the Control lens with respect to high luminance low contrast Distance Monocular Visual Acuity (logMAR) post lens fitting. A non-inferiority margin of 0.05 logMAR will be used.
- 2. The Test lens will be non-inferior to the Control lens with respect to low luminance high contrast Distance Monocular Visual Acuity (logMAR) post lens fitting. A non-inferiority margin of 0.05 logMAR will be used.

#### 3. TARGETED STUDY POPULATION

#### 3.1. General Characteristics

Subjects aged 18 to 39 years (inclusive) who are habitual soft contact lens wearers will be recruited for this clinical study. Subjects must meet all the inclusion and none of the exclusion criteria listed in Section 3.2.

#### 3.2. Inclusion Criteria

Potential subjects must satisfy all of the following criteria to be enrolled in the study:

- 1. The subject must read, understand, and sign the STATEMENT OF INFORMED CONSENT and receive a fully executed copy of the form
- 2. Appear able and willing to adhere to the instructions set forth in this clinical protocol
- 3. Subjects between 18 and 39 (inclusive) years of age at the time of screening
- 4. Be a current soft contact lens wearer in both eyes with a minimum of 6 hours/day and 5 days/week over the last month by self-report
- 5. The subject must be willing to be photographed and/or video-taped.

#### Eligibility after Baseline:

- 6. The subject's vertex corrected spherical equivalent distance refraction must be in the range of -1.00 D to -6.00 D (inclusive) in each eye
- 7. The subject's refractive cylinder must be less than or equal to 0.75 D (inclusive) in each eve
- 8. Have spherical best corrected visual acuity of 20/25 or better in each eye.

#### 3.3. Exclusion Criteria

Potential subjects who meet any of the following criteria will be excluded from participating in the study:

Exclusion Criteria after Screening:

- 1. Currently pregnant or lactating
- 2. Any systemic disease (eg, Sjögren's Syndrome), allergies, infectious disease (eg, hepatitis, tuberculosis), contagious immunosuppressive diseases (eg, HIV), autoimmune disease (eg rheumatoid arthritis), or other diseases, by self-report, which are known to interfere with contact lens wear and/or participation in the study (at the investigators discretion)
- 3. Use of systemic medications (eg, chronic steroid use) that are known to interfere with contact lens wear (at the investigators discretion)
- 4. Any previous, or planned (during the study) ocular surgery (eg, radial keratotomy, PRK, LASIK, etc.)
- 5. Participation in any contact lens or lens care product clinical trial within seven (7) days prior to study enrollment

6. Employee or family members of clinical site (eg, Investigator, Coordinator, Technician).

#### Exclusion Criteria after Baseline

- 7. Any ocular allergies, infections or other ocular abnormalities that are known to interfere with contact lens wear and/or participation in the study. This may include, but not be limited to entropion, ectropion, extrusions, chalazia, recurrent styes, glaucoma, history of recurrent corneal erosions, aphakia, or corneal distortion (at the investigators discretion)
- 8. Clinically significant (Grade 3 or 4 on FDA scale) tarsal abnormalities, bulbar injection, corneal edema, corneal vascularization, corneal staining, or any other abnormalities of the cornea which would contraindicate contact lens wear.

#### 3.4. Enrollment Strategy

Study subjects will be recruited from the Institution/clinical site's subject database and/or utilizing Independent Ethics Committee (IEC) or Institutional Review Board (IRB) approved materials by a market research company.

#### 4. STUDY DESIGN AND RATIONALE

#### 4.1. Description of Study Design

This is a single-visit, bilateral, randomized, controlled, 2 (lens)  $\times$  2 (period) crossover, non-dispensing study. Up to 40 subjects will be enrolled with the target of approximately 34 to complete the study.

If a subject meets all eligibility criteria, they will be randomized to one of two lens wear sequences (Test/Control or Control/Test) in a bilateral fashion; otherwise they will be screen failed. Subjects will not be masked to the variant/pattern of the lenses due to visible differences in the study lenses; however, subjects will be masked to the lens brands. There will be a 5-minute washout period between study lenses.

#### 4.2. Study Design Rationale

Crossover designs are a well-established study design in which subjects are exposed to multiple treatments during different time periods. A 2×2 bilateral crossover design was considered to be the optimal design since the study period is short the design can be cost effective and more efficient comparisons between treatments can be made than compared a parallel study since fewer subjects are required to achieve the same pre-specified statistical power. Each subject will act as their own control to reduce the influence of potential confounding factors such as age, gender and vision correction. Only a 5-minute washout between study lens wear will be implemented to help reduce any potential bias, since this is a non-dispensing study.

#### 4.3. Enrollment Target and Study Duration

Approximately 40 subjects ages 18 to 39 years (inclusive) who are habitual soft contact lens wearers will be enrolled in this single-visit clinical study with the goal of 34 subjects to complete. While both male and female patients are eligible to participate, we will aim to enroll female subjects ages 18-29 years.

Enrollment is defined as execution of the informed consent form.

#### 5. TEST ARTICLE ALLOCATION AND MASKING

#### 5.1. Test Article Allocation

The study lenses will be worn in a bilateral and random fashion using a 2×2 crossover design. A computer-generated randomization scheme will be used to randomly assign subjects, in block of 4, to one of the two possible lens wear sequences: Test/Control or Control/Test. The random scheme will be generated using the PROC PLAN procedure from Statistical Analysis System (SAS) Software Version 9.4 or higher (SAS Institute, Cary, NC).

The study site must follow the randomization scheme provided and complete enrollment per the randomization list and not pre-select or assign subjects. The randomized assignment of subjects will be performed at the first visit prior to the first fitting. The following must have occurred prior to randomization:

- o Informed consent has been obtained
- O Subject meets all the inclusion / exclusion criteria
- Subject history and baseline information has been collected.

#### 5.2. Masking

Due to visible print differences, subjects and investigators will be aware of the different patterns/variants of the investigational product. However, subjects will be masked to the lens brand to prevent bias during the lens discussions.

Under normal circumstances, the mask should not be broken until all subjects have completed the study and the database is finalized. Otherwise, the mask should be broken only if specific emergency treatment/course of action would be dictated by knowing the treatment status of the subject. In such cases, the Investigator may, in an emergency, contact the medical monitor. In the event the mask is broken the Sponsor must be informed as soon as possible. The date, time, and reason for the unmasking must be documented in the subject record. The Investigator is also advised not to reveal the study treatment assignment to the clinical site or Sponsor personnel.

Subjects who have had their treatment assignment unmasked are expected to return for all remaining scheduled evaluations. Subjects who are discontinued may be replaced.

#### 5.3. Procedures for Maintaining and Breaking the Masking

The Clinical Supply Unit will generate a unique code for all study lenses. Marketed products and investigational lenses will have nearly identical labels, differing only in the product specifications and lens code, to maintain masking. Subjects will be dispensed lenses by the lens code in accordance with the randomization scheme provided by the study statistician.

The test articles mask shall not be broken unless information concerning the lens type is necessary for the urgent medical treatment of a subject. The Sponsor must be notified before the mask is broken.

When dispensing test articles, the following steps should be followed to maintain randomization codes:

- Investigator or designee (documented on the Delegation Log) will consult the lens fitting schedule/randomization scheme to obtain the test article assignment for that subject prior to dispensing.
- Investigator or designee will record the subject's number on the appropriate line of the randomization scheme.
- 3. Investigator or designee will pull the appropriate test articles from the study supply. All test articles that are opened, whether dispensed (placed/fit on eye or dispensed outside the clinical site) or not, must be recorded on the Test Article Accountability Log in the "Dispensed" section.

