1.9	Subjective Best Sphere Refraction	Perform subjective best sphere refraction with a phoropter (adopt the maximum plus to maximum visual acuity (MPMVA) approach and use the duo-chrome test for binocular balancing) and record the best corrected distance visual acuity (OD, OS, OU) to the nearest letter.  Note: The endpoint criterion for the duo-chrome test is the lens power at which the red and green sides of the chart appear to be equally distinct. However, if the subject's response changes from "red" to "green" with only a 0.25D change in power and no report that the two sides appear to be equally sharp, the refraction endpoint should be the lens power that leave the red chart sharper.  Note 2: The subject's optimal vertexed spherical equivalent distance correction must be between -1.00D and -6.00D.	
1.10	Slit Lamp Findings	FDA Slit Lamp Classification Scale will be used to grade the findings and determine eligibility.  If any of these slit lamp findings are Grade 3 or higher, the subject may not continue at this time, but may return up to one additional time to determine eligibility. If discontinued a final examination must be completed.  If the clearance of the fluorescein needs to be expedited, preservative-free rewetting drops or saline may be instilled.	
1.11	Eligibility after Baseline	All responses to Inclusion Criteria questions must be answered "yes" and all responses to Exclusion Criteria questions must be answered "no" for the subject to be considered eligible.	

	Visit 1: Treatment 1 Lens Fitting			
Step	Procedure	Details		
1.12	Lens Selection	Assign the study lens based on the randomization scheme. Select the contact lens power based on subjective best sphere refraction.		
1.13	Lens Insertion	The Investigator or the subject inserts the study lenses. Record the time of lens insertion.  Check for lens damage under the slit lamp before proceeding with lens settling.  Replace damaged lenses if applicable.  Note: Designated site staff should observe the insertion process. If it appears that the subject attempts to insert a lens that is "inside-out", they should interfere to avoid incorrect insertion.		
		Note 2: If the lens moves excessively on the eye after insertion, ask the subject to remove the lens, confirm lens is not inverted (correct if it is is) and reinsert.		
1.14	Lens Settling	Allow the study lenses to settle for a minimum of 5 minutes.		

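### No concealment step is described: a site-held list, a printed block size of 4 and visibly different lenses let the next lens sequence be foreseen (minor, cheap to fix)

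*Combined protocol and SAP*

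**What the plan says.** Section 5.1 describes a computer-generated scheme that will "randomly assign subjects, in block of 4, to one of the two possible lens wear sequences: Test/Control or Control/Test". On its use it says: "The study site must follow the randomization scheme provided and complete enrollment per the randomization list and not pre-select or assign subjects". It also says: "The randomized assignment of subjects will be performed at the first visit prior to the first fitting", and it lists consent, eligibility and collection of history and baseline data as conditions to be met before randomisation.

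Section 5.3 gives the working steps. The investigator or designee "will consult the lens fitting schedule/randomization scheme to obtain the test article assignment for that subject prior to dispensing", then "will record the subject's number on the appropriate line of the randomization scheme". Lenses carry codes and nearly identical labels.

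Section 5.2 states that "subjects and investigators will be aware of the different patterns/variants of the investigational product". Section 6.4 says that over-labelling masks the investigators. The two statements conflict and should be reconciled, but a label cannot hide a printed pattern once the lens is on the eye.

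On entry decisions, exclusion criteria 2, 3 and 7 (Section 3.3) are left to the investigator's discretion. Step 1.10 in Section 7.2 adds that, when a slit lamp finding is Grade 3 or higher, "the subject may not continue at this time, but may return up to one additional time to determine eligibility".

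Nowhere do the documents say who is prevented from seeing later assignments, or how.

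**The concern.** The staff who judge eligibility also handle the randomisation scheme. Writing a subject number on a line implies a list with several lines. Lens codes give little protection, because the visible print would reveal which code is which after the first fittings. Even if later lines are covered, the block size is in the protocol and every past sequence has been observed.

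At stake is the comparability of the two sequence groups. Every subject wears both lenses, so what randomisation has to protect here is narrower than in a parallel trial: the two groups should have the same expected change between periods, for example from practice on the charts or tiredness over a 3.5-hour visit. If who enters depended on the next line, and that choice were related to this change, the lens estimate would shift. The sequence and period terms in the Section 14.5 model would not remove the shift, because in a 2x2 crossover a between-sequence difference in period change is the same contrast as the lens effect.

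**Working it through.** The plan gives no figure on predictability, so there is none to reproduce.

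**1. Predictability with a known block of 4.** Inputs: two sequences, 1:1, one block size of 4 (Section 5.1), past sequences seen. The six possible blocks are equally likely.

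| Place in block | Known with certainty | Best guess correct |
|---|---|---|
| 1st | 0 | 1/2 |
| 2nd | 0 | 2/3 |
| 3rd | 1/3 (first two alike) | 1/3 + (2/3)(1/2) = 2/3 |
| 4th | 1 | 1 |
| Mean | 1.333/4 = 33.3% | 2.833/4 = 70.8% |

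That is about 11 of 34 or 13 of 40 assignments certain, and 71% guessable against 50% by chance. If later lines can be read, the figure is 100% and the block size is irrelevant.

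**2. What varying the blocks buys.** Simulating blocks of 4, 6 and 8 in random order over 40 subjects, with a guesser who knows the set of sizes but not which is in use, gives about 2% certain and 67.5% guessable. Certainty nearly disappears; guessability falls only from 71% to 67.5%. Most of the protection must come from hiding later lines.

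**3. Effect on the lens comparison.** Let τ be Test minus Control, and δ the mean period-2 minus period-1 change in a sequence group.

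- Test/Control group: period 1 minus period 2 = τ − δ(TC).
- Control/Test group: period 2 minus period 1 = τ + δ(CT).
- Average of the two: τ + [δ(CT) − δ(TC)]/2.

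A subject's acuity level drops out. In a simulation with 17 per sequence, a common period effect of 0.02 logMAR and sequence means 0.10 logMAR apart in level, the estimate stayed at 0.000 (SE 0.019). Only a between-sequence difference in period change matters, and half of it passes into the estimate.

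**4. Illustration only.** The documents give no period effect and no selection effect. Assume mean period changes differ by 0.02 logMAR (one letter) in the direction that favours Test. The shift is 0.02/2 = 0.01, or 0.01/0.05 = 20% of the margin. From Section 14.2 (SDs 0.09041 and 0.09454, correlation 0.30 between periods, eyes perfectly correlated) with 34 completers:

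- SD of the within-subject difference: 0.09041 × √1.4 = 0.107; 0.09454 × √1.4 = 0.112.
- SE: 0.107/√34 = 0.0183; 0.112/√34 = 0.0192.
- Chance of falsely declaring non-inferiority at a true difference of 0.05 (two-sided 95% limit, noncentral t, 32 df): 2.5% with no shift, 4.4–4.5% with a 0.005 shift, 7.3–7.6% with a 0.01 shift.

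These rates are per lighting condition. Section 2.3 requires both to pass, so the study-level rate is no higher.

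**5. How much selection that would take.** A difference of 0.02 is 0.02/0.112 to 0.02/0.107, or 0.18 to 0.19 SD of change. Suppose all 6 places between 40 enrolled and 34 completing were used to reject the extreme 3 of 20 (15%) in opposite directions in each sequence, with no dropouts. By the large-sample normal truncation formula this moves each group by 0.2332/0.85 = 0.274 SD on the trait used, so 0.55 SD apart. That trait would have to correlate about 0.18/0.55 = 0.33 to 0.19/0.55 = 0.34 with the future period change. Choosing or reordering subjects before consent is not capped in this way, but it too needs a predictor of change.

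**The case against.** The strongest reply is that Section 5.1 already has the two rules that matter: eligibility and baseline come before randomisation, and pre-selection is forbidden. The Section 5.3 look-up is for one subject, just before dispensing, and so follows acceptance. This stands as a description of the procedure. It does not close the gap, because neither rule hides the next line during a discretionary judgement.

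A reader might infer that the site holds the complete open list, so that each sequence is in fact known before a subject is accepted. The documents do not say this. Recording a subject number on a line suggests a multi-line list, but whether later lines are visible is not stated. The text supports only that the next sequence can be known.

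The return provision in step 1.10 is limited to findings of Grade 3 or higher and is not a general means of bringing a subject back later. Nor do the documents link the discretionary criteria to change in acuity between periods.

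The crossover objection largely stands. Order is all that is randomised, level differences cancel, and the baseline assessments (Snellen acuity, refraction, slit lamp) are not shown to predict period change. Acuity measurement by staff who can see the lens pattern is probably the larger source of bias, and concealment would not cure it.

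**Conclusion.** The point holds as a minor gap in procedure. Sections 5.1 to 5.3 describe no way of hiding later assignments, and the next sequence can be foreseen: fully if later lines are visible, otherwise 33% with certainty and 71% by best guess. The last two figures assume that staff know the printed block size and the past sequences.

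The risk to the result is small and cannot be sized from the documents. A reader might take the 7.3–7.6% error rate as the expected consequence. It is not. It requires selection by sequence on a future change that nothing measured at baseline is shown to predict, and in the direction that favours Test. Without such selection the bias is zero. The reason to act is that a confirmatory trial can close the gap at almost no cost.

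**What to change.** Main change, Section 5.3: have the statistician or the Clinical Supply Unit hold the list. The site receives one assignment at a time, by sequentially numbered sealed envelope or through the EDC system named in Section 15.1 if it can be set up for this, and only after eligibility after baseline (step 1.11) is recorded as met.

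Supporting change, Section 5.1: remove the block size from the protocol and site documents, and generate randomly varying sizes (for example 4, 6 and 8) in the same PROC PLAN program. On its own this would do little for guessability.

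The cost is about 40 envelopes or one EDC field, plus a few lines of code and text. The downside is a possible imbalance between sequences at the end, at most 4 subjects with a largest block of 8. For 34 completers split 19 and 15, the variance factor against an even split is (34/4)(1/19 + 1/15) = 1.014, a loss of about 1.4%. No subjects, visits or assessments are added.
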